Study Procedures	Comments	PHASE Screening Phase Up to 28 days before Randomization	Treatment Phase (4-week cycles \pm 3 days)				EOT Visit 30 \pm 3 days after last dose	Posttreatment Follow-up Phase Survival Follow-up Every 12-16 weeks
			Cycle 1 Day 1 (pre-dose)	Cycle 1 Day 8, 15, 22	Cycle 2 Day 1, 8, 15, 22	Cycle 3 until EOT Day 1		
FACT-An	See Attachment 6; At all visits, complete before any tests, procedures, dosing or other consultations are performed and before the subject is informed of any assessment results (eg, hemoglobin values), when possible.		X		X (D1 only)	X	X	X (until start of subsequent therapy)
EQ-5D-5L	See Attachment 7; At all visits, complete before any tests, procedures, dosing or other consultations are performed and before the subject is informed of any assessment results (eg, hemoglobin values), when possible.		X		X (D1 only)	X	X	X (until start of subsequent therapy)
QUALMS	See Attachment 8. At all visits, complete before any tests, procedures, dosing or other consultations are performed and before the subject is informed of any assessment results (eg, hemoglobin values), when possible.		X		X (D1 only)	X	X	X (until start of subsequent therapy)
PGIC	See Attachment 9. At all visits, complete before any tests, procedures, dosing or other consultations are performed and before the subject is informed of any assessment results (eg, hemoglobin values), when possible.				X (D1 only)	X	X	X (until start of subsequent therapy)
Survival status and subsequent anti MDS/AML therapy	Survival status and subsequent therapy are planned to be collected at the EOT visit and throughout survival follow-up period at least every 12 to 16 weeks (data may be collected more frequently, if needed).						X	X
Clinical Laboratory Assessments								
Chemistry (local laboratory)	Screening tests should be performed within 14 days prior to Randomization. For C1D1, no need to repeat if Screening tests performed within 5 days. After C1D1, tests must be performed within 48h before the scheduled visit. Refer to Inclusion Criteria (Section 4.1) for further details. Refer to Sections 9.8 and 9.8.1 for additional detail on required clinical laboratory testing.	X	X	X	X (D1 only)	X	X	

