Chemistry panel for LFT investigations (local laboratory)	Includes GGT, chloride, bicarbonate, magnesium, and fractionated bilirubin. For subjects with AST, ALT, ALP or bilirubin Grade \geq 3, repeat chemistry panel and LFT investigations panel weekly until bilirubin with fractionation is $<$ 3x ULN, and AST, ALT and ALP is $<$ 5x ULN. Subjects with Grade 1 or Grade 2 elevations in AST, ALT, ALP or bilirubin at time of treatment discontinuation should continue to have tests monthly until resolution to at least baseline grade or until the start of subsequent therapy, whichever comes first.		If an adverse event of interest occurs		
INR (or PT) and aPTT (local laboratory)	Additional assessments performed during treatment phase if subject has a hemorrhagic event.		Repeat during study if subject has a Grade \geq 3 bleeding event		
Serum or urine pregnancy test			X	X	
Concomitant Therapy			X	X	
Adverse Events	Adverse events, including SAE, pregnancy, and AEI monitoring, will continue in the Extension Phase		X	X	
Survival Status and Subsequent Anti-MDS/AML Therapy	Survival status and subsequent therapy are planned to be collected throughout the survival follow-up approximately 16 weeks (data may be collected more frequently, if needed).			X	X
Disease Progression Follow-up	Per modified IWG 2006; see Attachment 5. Data to be collected includes date of disease progression to AML, and any available supporting bone marrow, peripheral blast, and laboratory results.		Continuous		Until progression to AML

AE = adverse event; AEI = adverse event of interest; AML = acute myeloid leukemia; DBP = diastolic blood pressure; EOT = end of treatment; IWG = International Working Group; MDS = myelodysplastic syndrome; q = every; SAE = serious adverse event; SBP = systolic blood pressure

ABBREVIATIONS

AE	adverse event
AEI	adverse events of interest
aPTT	activated partial thromboplastin time
ALP	alkaline phosphatase
ALT	alanine aminotransferase
AML	acute myeloid leukemia
ANC	absolute neutrophil count
AST	aspartate aminotransferase
AUC	area under the curve
BM	bone marrow
CFU-MK	colony-forming unit-megakaryocyte
C _{max}	maximum plasma concentration
CMML	chronic myelomonocytic leukemia
CR	complete remission
CRF	case report form
CSC	circulating stem cells
CytoF	cytometry by time of flight
DMC	Data Monitoring Committee
DNA	deoxyribonucleic acid
ECG	electrocardiogram
ECOG	Eastern Cooperative Oncology Group
eCRF	electronic case report form
EOT	end of treatment
EPO	erythropoietin

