4.1. Inclusion Criteria

Each potential subject must satisfy all of the following criteria to be entered in the study.

1. Man or woman ≥ 18 years of age (or the legal age of consent in the jurisdiction in which the study is taking place);
2. Criterion modified per Amendment 1.
 - 2.1. Criterion modified per Amendment 2.
 - 2.2. Criterion modified per Amendment 3
 - 2.3 In Part 1, diagnosis of MDS according to WHO criteria confirmed by bone marrow aspirate and biopsy within 12 weeks prior to C1D1. A local laboratory report from this diagnostic bone marrow aspirate and biopsy must be reviewed and approved by the sponsor (Attachment 1).

In Part 2, diagnosis of MDS according to WHO criteria confirmed by bone marrow

aspirate and biopsy within 12 weeks prior to Randomization (Attachment 1). A sample of the baseline bone marrow aspirate and biopsy must be submitted to the Independent Central Pathology Reviewer for diagnostic confirmation. Central laboratory review is required to confirm diagnosis prior to Randomization.

3. IPSS low or intermediate-1 risk MDS (Attachment 3);
4. Criterion modified per Amendment 1.
 - 4.1. RBC transfusion dependent, defined as requiring at least 4 RBC units transfused over an 8-week period during the 16 weeks prior to C1D1 (Part 1) or Randomization (Part 2) (defined in Section 3.1); pre-transfusion Hb should be ≤ 9.0 g/dL to count towards the 4 units total;
5. Has MDS that is relapsed/refractory to ESA treatment; as defined by meeting any one of the criteria below:
 - 5.1. Received at least 8 weeks of treatment with a minimum weekly dose of epoetin alfa 40,000 U, epoetin beta 30,000 U or darbepoetin alfa 150 mcg (or equivalent agent/dose), without having achieved a Hb rise ≥ 1.5 g/dL or decreased RBC transfusion requirement by at least 4 units over 8 weeks
 - 5.2. Criterion 5.2 replaced by criterion 5.2.1 per Amendment 5.
 - 5.2.1 Transfusion dependence or reduction in Hb by ≥ 1.5 g/dL after hematologic improvement from at least 8 weeks of treatment with therapies outlined in inclusion criteria 5.1, in the absence of another explanation.
 - 5.3. Criterion 5.3 replaced by criterion 5.4 per Amendment 1.
 - 5.4. Endogenous serum EPO level >500 mU/mL;
6. Criterion modified per Amendment 1.

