9.1.5. Posttreatment Phase (Follow-Up)

The Posttreatment Follow-up Phase is the time between the End-of-Treatment Visit and the end of study participation or end of study. During this phase, contact will be made as detailed in the Time and Events Schedules (Table 1 and Table 3) until the subject has died, is lost to follow-up, or has withdrawn consent.

If study drug is discontinued for any reason other than disease progression, a response assessment should be performed at the time of suspected disease progression.

Collection of transfusion data should continue every 4 to 6 weeks until the first transfusion in the posttreatment follow-up phase.

If the information on survival status and subsequent therapy is obtained via telephone contact, then written documentation of the communication must be available for review in the source documents. If the subject has died, then the date and cause of death will be collected and documented on the eCRF. Where allowed by local law, public records may be used to document death for the purpose of obtaining survival status.

As per the Time and Events Schedule for the main study of Part 2 (Table 3), sites should attempt to administer the PRO questionnaires before any tests, procedures, or other consultations are

performed, when possible, (see Section 9.6). Subjects who visit the site for the follow-up assessments should complete the questionnaires at that time. If the assessments are conducted via a telephone call with the subject, then the subject's questionnaire responses will be read over the telephone to the site staff who will record the data in the questionnaires. If the subject is unable to complete the assessments during the Posttreatment Follow-up Phase, then the reason for not completing the questionnaires will be documented (eg, too ill, subject refused). Subjects will be required to complete PRO questionnaires in posttreatment follow-up until the start of subsequent therapy.

The sponsor will ensure that subjects benefiting from treatment with imetelstat will be able to continue treatment after the End of the Study. Subjects who were assigned to the placebo arm in the main study will be instructed that they should return to their primary physician to determine standard of care.

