9.2.2. Secondary Endpoints

- Safety of imetelstat in subjects with MDS (eg, incidence, intensity, and type of adverse events, vital signs measurements, clinical laboratory values, ECGs changes, and deaths);
- 24-week RBC TI rate, defined as the proportion of subjects without any RBC transfusion during any consecutive 24 weeks (168 days) starting from Study Day 1;
- Time to the 8-week (24-week) RBC TI, defined as the interval from Study Day 1 to the first day of the first 8-week (24-week) RBC TI period;
- Duration of RBC TI, defined as the first day of the longest RBC TI period to the date of the first RBC transfusion after the TI period starts;
- Rate of hematologic improvement, including HI-E, per modified IWG 2006;
- Rates of CR, PR, or mCR per modified IWG 2006;
- OS, defined as the interval from Study Day 1 to death from any cause. Survival time of living subjects will be censored on the last date a subject is known to be alive or lost to follow-up;
- Progression free survival, defined as the time interval from Study Day 1 to the first date of disease progression or death from any cause, whichever occurs first. For subjects who do not have documented disease progression and who are still alive at the end of the study or clinical cutoff will be censored at the last disease evaluation date.
- Time to progression to AML, defined as the interval from Study Day 1 to the date of AML diagnosis. For subjects who have not progressed to AML and are still alive at the cutoff date for the analysis or who withdraw from the study (withdrawal of consent or lost to follow-up), data will be censored at the date of the last disease evaluation;
- Amount and relative change in RBC transfusions;
- Rate of myeloid growth factors usage, defined as the proportion of subjects receive any myeloid growth factors starting from Study Day 1; duration of myeloid growth factor administered starting from Study Day 1;
- Assessment of QUALMS, FACT-An, and EQ-5D-5L;

- Pharmacokinetic parameters (eg, C_{max} , AUC_{0-t}), and immunogenicity of imetelstat (eg, antibodies to imetelstat);
- Medical resource utilization data including hospitalization, emergency room visits, and hematology specialist visits ;
- ECG parameters including change in QT interval by Fridericia's correction method ($\Delta QTcF$) in the Ventricular Repolarization substudy (Part 2 only).

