10.2. Discontinuation of Study Treatment

If a subject is experiencing clinical benefit in the study without significant toxicity that puts the subject at risk, or routine noncompliance that puts the study outcomes at risk, investigators should consider continuing the subject on treatment. If a subject shows evidence of progressive disease, but the investigator feels they are still experiencing clinical benefit from imetelstat, the sponsor should be contacted to discuss potential continuation of treatment. If a subject's study treatment must be discontinued, the event will not result in automatic withdrawal of the subject from the study and investigators should reinforce the need for subjects to stay in the study for survival follow-up.

A subject's study drug should be discontinued if:

- The investigator believes that for safety reasons (eg, adverse event or subject experiences unacceptable toxicity) it is in the best interest of the subject to discontinue study treatment
- The subject becomes pregnant
- The subject experiences overt disease progression or relapse
- The subject refuses further treatment
- A serious protocol violation has occurred, as determined by the principal investigator or the sponsor

End-of-Treatment and posttreatment follow-up assessments should be obtained. The reason(s) a subject discontinues treatment will be recorded on the eCRF.

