Attachment 3: International Prognostic Scoring System (IPSS) for Myelodysplastic Syndrome

Prognostic Variable	Survival and AML Evolution Score Value				
	0	0.5	1.0	1.5	2.0
Marrow Blasts (%)	<5	5 to 10	n/a	11 to 20	21 to 30
Karyotype ^a	Good	Intermediate	Poor	N/A	N/A
Cytopenias: Neutrophil count <1800/ μ L Platelets <100,000/ μ L Hemoglobin <10 g/dL	0 or 1	2 or 3	N/A	N/A	N/A

a Good: normal or any one of the following: -Y, del 5q, del 20q; Intermediate: any other abnormality; Poor: chromosome 7 abnormalities, complex, ≥ 3 abnormalities N/A = not applicable.
					

Risk Category:	Combined Score (Sum of Marrow Blast + Karyotype + Cytopenia Score)
Low	0
Intermediate-1	0.5 to 1.0
Intermediate-2	1.5 to 2.0
High	≥ 2.5

SOURCE: Greenberg P, Cox C, LeBeau MM, et al. International scoring system for evaluating prognosis in myelodysplastic syndromes. Blood 1997;89:2079-2088.

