Disease progression	For patients with: $<5\%$ blasts: $\geq 50\%$ increase in blasts to $>5\%$ blasts $5\%–10\%$ blasts: $\geq 50\%$ increase to $>10\%$ blasts $10\%–20\%$ blasts: $\geq 50\%$ increase to $>20\%$ blasts $20\%–30\%$ blasts: $\geq 50\%$ increase to $>30\%$ blasts Any of the following: $\geq 50\%$ decrement from maximum remission/response in granulocytes or platelets Reduction in Hb by ≥ 2 g/dL Transfusion dependence

* Dysplastic changes should consider the normal range of dysplastic changes (modification).

† Modification to IWG response criteria.

‡ In some circumstances, protocol therapy may require the initiation of further treatment (eg, consolidation, maintenance) before the 4-week period. Such patients can be included in the response category into which they fit at the time the therapy is started. Transient cytopenias during repeated chemotherapy courses should not be considered as interrupting durability of response, as long as they recover to the improved counts of the previous course.

Attachment 5: (Continued): International Working Group (IWG) Response Criteria 2006**Proposed modified International Working Group response criteria for hematologic improvement**

Hematologic Improvement*	Response criteria (responses must last ≥ 8 weeks)†
Erythroid response (pretreatment, < 11 g/dL)	Hb increase by ≥ 1.5 g/dL Relevant reduction of units of RBC transfusions by an absolute number of at least 4 RBC transfusion units/8 weeks compared with the pretreatment transfusion number in the previous 8 weeks. Only RBC transfusions given for a Hb of ≤ 9 g/dL pretreatment will count in the RBC transfusion response evaluation†
Platelet response (pretreatment, $< 100 \times 10^9/L$)	Absolute increase of $\geq 30 \times 10^9/L$ for patients starting with $> 20 \times 10^9/L$ platelets Increase from $< 20 \times 10^9/L$ to $> 20 \times 10^9/L$ and by at least 100%†
Neutrophil response (pretreatment, $< 1 \times 10^9/L$)	At least 100% increase and an absolute increase $> 0.5 \times 10^9/L$ †
Progression or relapse after HI‡	At least 1 of the following: At least 50% decrement from maximum response levels in granulocytes or platelets Reduction in Hb by ≥ 1.5 g/dL Transfusion dependence

* Pretreatment counts averages of at least 2 measurements (not influenced by transfusions) ≥ 1 week apart (modification).

† Modification to IWG response criteria.

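### Main-study follow-up has no scheduled item for AML status or date once drug is stopped for progression, so AML arising later is censored rather than counted

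*Protocol*

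**What the plan says.** - **Endpoint.** Protocol 9.2.2: "Time to progression to AML, defined as the interval from Study Day 1 to the date of AML diagnosis". Subjects without AML who are alive at the cutoff, or who withdraw, are censored at their last disease evaluation. Protocol 11.4 and SAP 4.9.3.2 plan a stratified log-rank test and a hazard ratio.
- **Stopping drug.** Protocol 10.2 lists among the reasons: "The subject experiences overt disease progression or relapse". Treatment beyond progression is possible after discussion with the sponsor.
- **Assessments.** In Table 3 and 9.1.4, scheduled response assessments and marrows run up to and including suspected progression. After that, 9.1.5 provides: "If study drug is discontinued for any reason other than disease progression, a response assessment should be performed at the time of suspected disease progression".
- **Follow-up contacts.** Table 3, every 12 to 16 weeks: "Survival status and subsequent therapy are planned to be collected at the EOT visit and throughout survival follow-up period". Transfusions are recorded until the first one in follow-up, questionnaires until the next therapy, and date and cause of death when a subject dies.
- **Extension Phase.** Table 5 has a Disease Progression Follow-up row that continues until AML: "Data to be collected includes date of disease progression to AML". The phase starts 24 months after the last main-study randomization and needs an updated consent (9.1.6).
- **SAP 4.9.3.1.** A subject who starts subsequent anti-cancer therapy before documented progression is censored at the last evaluable response assessment, or progression status, on or before that therapy.

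**The concern.** The 9.1.5 instruction covers subjects who stopped drug for some other reason. For those who stopped because of progression, the main-study schedule has no later point at which AML status or a diagnosis date is requested. Adverse event reporting does not fill the gap: under 12.3.1, progression of MDS is not reported as an adverse event, and routine collection ends 30 days after the last dose.

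The clock for this endpoint therefore stops because the disease has worsened, which makes the censoring informative. Ascertainment can also differ by arm. After the unblinding that follows the primary analysis, imetelstat subjects may stay on drug with scheduled marrows, while placebo subjects may stop and move to follow-up (3.2). At stake are an undercount of AML and a hazard ratio that depends partly on when and why subjects stopped drug.

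**Working it through.** The documents give no event count or power for time to AML, so there is no figure of theirs to reproduce. The check has four steps.

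**1. Blasts at entry.** Section 4.1 admits IPSS low or intermediate-1, a combined score of at most 1.0 (Attachment 3). The score is blasts + karyotype (0, 0.5 or 1.0) + cytopenias (0 or 0.5).
- Blasts <5% (0 points): eligible totals 0, 0.5 and 1.0.
- Blasts 5-10% (0.5 points): eligible totals 0.5 and 1.0.
- Blasts 11-20% (1.5 points): lowest total 1.5 + 0 + 0 = 1.5, which is intermediate-2 and not eligible.

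On the bands as written, every eligible subject enters with 10% blasts or fewer.

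**2. Where progression is declared.** Attachment 5 requires a rise of at least 50% to above 5% (baseline <5%) or above 10% (baseline 5-10%). The trigger is max(1.5 × baseline, 5) or max(1.5 × baseline, 10).
- Baseline 1-3%: just above 5%.
- Baseline 4%: 1.5 × 4 = 6%.
- Baseline 5-6%: just above 10%.
- Baseline 8%: 1.5 × 8 = 12%.
- Baseline 10%: 1.5 × 10 = 15%. Exactly 10% also fits the 10-20% band, where progression needs more than 20%.

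Attachment 1 still classes 10-19% marrow blasts as MDS. Taking AML as 20% or more (inferred; neither document states a cut-off), blast progression is declared 5 to 15 percentage points earlier, apart from that edge case. Hemoglobin, granulocyte, platelet or transfusion grounds can also trigger progression.

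**3. One subject traced through the rules.** Blasts rise from 3% to 8%; progression is declared and drug is stopped. Scheduled assessments end, and 9.1.5 does not call for another. AML is diagnosed six months later. No main-study item asks for it. If the subject is alive at the cutoff, 9.2.2 censors at the last disease evaluation, which is the progression visit. If subsequent therapy came first, SAP 4.9.3.1 censors at or before that therapy, reading documented progression there as progression to AML. If the subject has died, neither text gives a censoring date, but no AML event is on file.

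**4. Scale, as an illustration.** Protocol 1.1.4 cites AML in 12-20% over 5 years after early ESA failure. At constant hazard, incidence by year t is 1 − (1 − p)^(t/5). At 2 years:
- p = 0.12: 1 − 0.88^0.4 = 0.0498, and 170 × 0.0498 = 8.5.
- p = 0.20: 1 − 0.80^0.4 = 0.0854, and 170 × 0.0854 = 14.5.

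That is about 8 to 15 events. The share arising after a progression stop is not given anywhere.

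**The case against.** - **Much AML is already captured.** This is true of AML present in the marrow at suspected progression, AML in a subject kept on drug beyond progression, and AML found at the suspected-progression assessment after another stop reason. Table 5 is not limited to AML arising after Extension entry, so it may recover earlier dates for subjects who are alive and re-consent, though only after the main-study analyses. A reader might infer that the endpoint misses transformations in general; the documents do not support that.
- **The SAP would not count some of these events anyway.** This stands. AML after subsequent anti-cancer therapy is censored by rule, so collecting the date does not by itself bring it into the analysis.
- **A status item may exist on the eCRF.** The SAP names progression status separately from response assessment, and the eCRF is not among the documents. The gap is established for the protocol schedule only.
- **Indirect evidence exists.** Subsequent anti-MDS/AML therapy and cause of death point to some cases, but neither supplies a diagnosis date. Tabulating censoring reasons, as planned, recovers no events.
- **The scale is loose.** The 12-20% applies to early ESA failure, whereas 4.1 sets no such limit and also admits subjects on serum EPO above 500 mU/mL alone. The calculation ignores death and dropout. Taking an assumed share such as 25-75% would give a count of lost events, but nothing in the documents supports that share. Nor do they support a claim that AML risk peaks at the moment of censoring, or that the hazard ratio moves by a stated amount.

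**Conclusion.** The gap is real and should be closed. Following the main-study schedule as written, AML that arises after a progression stop is censored at or near the progression evaluation in the main-study analyses. The loss is permanent for subjects who die, are lost to follow-up or do not re-consent before the Extension Phase.

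The number lost cannot be derived. About 8-15 AML events by 2 years is an illustration resting on a constant hazard and the early-ESA-failure rate. With totals of that order, losing a few would matter to the curve, but how many are lost is unknown. The conclusion also rests on an inferred 20% AML threshold and on the eCRF adding nothing beyond Table 3.

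A reader might infer that the trial's main claims are affected. They are not: under SAP 4.9.1.3 the tested secondary endpoints are 24-week TI, HI-E, PFS and OS, so time to AML carries no controlled type I error, and sample size is untouched.

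**What to change.** 1. Add the Table 5 Disease Progression Follow-up item to the Posttreatment column of Table 3 for all subjects, whatever the reason for stopping: AML yes/no, date of diagnosis and any available supporting results, at the existing 12-16-week contacts, until AML.
2. Query AML status once for all subjects already in or past follow-up, including those who have died. Do this before unblinding where still possible, otherwise before the final main-study analysis.
3. Reconcile the censoring text in protocol 9.2.2 and SAP 4.9.3.1, so that for subjects without AML the last AML-status contact counts as the last evaluation. State the date used for deaths without AML in the same edit.
4. The SAP may keep censoring at subsequent anti-cancer therapy, but should add a sensitivity analysis that counts AML regardless of subsequent therapy.

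The cost is one eCRF item at contacts already scheduled, one round of site queries, and short protocol and SAP edits. No marrow or visit is added. The downsides are that some AML dates will rest on local records, and any query made after the primary analysis will be open-label.
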